The study proposes to conduct a stepped-wedge, cluster-randomized implementation trial of a novel, user-centered implementation strategy for the delivery of TB contact investigation at 12 TB diagnostic and treatment units (DTUs) located at health facilities in central Uganda. The trial over will proceed over the course of 16 trial steps, each 8 weeks in duration, with the intervention period lasting from as little as 16 weeks up to 56 weeks at the participating facilities. We will use a complete stepped-wedge design, including an 8-week transition period for training and initial adoption, followed by 8 to 52 weeks of post-intervention data collection at each site. Data collected during the transition periods will not be included in the final analysis. In addition, the trial will be paused for 6 weeks during the annual 2022-2023 year-end holiday period (12 December 2022 through 15 January 2023; all transition periods falling during and after this pause period will be delayed by six weeks and patients recruited during this period, as well as the data of their contacts, will be excluded from the trial.[§] The rationale for this pause is that staffing levels and patient visits are low during this period, and without exclusion, this could bias the trial results in uncertain ways.

§Version 2.0 Update: On 15 October 2022, the President of Uganda announced Ebola-related public health restrictions preventing public movement in two districts where two study sites are located: Mubende and Kasambya. As a result, the principal investigators immediately paused all new introductions of the study intervention effective immediately for the subsequent 8-week period ending 11 December 2022, effectively extending the previously proposed 6-week study pause by at least 14 weeks. The original schema is shown below in Figure 1, and an updated schema is shown below in Figure 2.

[figure not shown]

Figure 1. HCD-CoP Intervention Randomization and Enrolment Schedule.

Legend: Ordinal numbers indicate the cross-over sequence from standard to the intervention period. Note that pause periods are not shown in the current figure.

Group	Site	Month																	
		1 Mar 7 - Apr 3	2 Apr 4 - May 1	3 May 2 - May 29	4 May 30 - Jun 26	5 Jun 27 - Jul 24	6 Jul 25 - Aug 21	7 Aug 22 - Sep 18	8 Sep 19 - Oct 16	9 Oct 17 - Nov 13	10 Nov 14 - Dec 11	Holiday	11 Dec 12 - Jan 15	12 Jan 16 - Feb 12	13 Feb 13 - Mar 12	14 Mar 13 - Apr 9	15 Apr 10 - May 7	16 May 8 - Jun 4	17 Jun 5 - Jul 2

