To inform our sample size calculations, we used a conservative estimate of the average number of index TB patients of 11 per clinic per 8-week block period (g), assuming a rho-alpha of 0.172 and rho-beta of 0.647 from our preliminary data, and an average number of symptomatic contacts per index TB case (m) of 1, as well as a pre-intervention proportion of patients completing treatment (p1) of 0.4, a post-intervention proportion of treatment completion (p2) of 0.6, the number of clusters crossing at each step (k) of 2, and total steps (steps) of 6.

Using the Stata command:

steppedwedgeTwoLevelsD, binomial complete(1) vartotal(1) p1(0.4) p2(0.6) m(1) k(2) rho(0.172) rho2(0.647) alpha(0.05) steps(6) g(11),

We estimate that the trial will conservatively need 924 total symptomatic contacts of index TB patients to achieve a power of 99%. Sample size estimates were reached using PASS 15 and Stata 16, with an extension to account for multiple levels of clustering as per Hemming et al.[3] and Davis-Plourde [4]. Although some sample size estimators predict 100% power, 100% power is not theoretically achievable, and therefore rendered as 99%. Because index patients and contacts are participants in routine services, we will not limit enrollment if it exceeds these numbers, which we project may be higher by four-fold or greater if the intervention strategy is highly effective.

Tests for Two Proportions in a Stepped-Wedge Cluster-Randomized Design

Design type: Complete

Test statistic: Wald Z-Test

$H_0: P_1 - P_2 = 0$.

$H_A: P_1 - P_2 = D_1 \neq 0$.

ICC (intra-cluster correlation coefficient (rho)) measures the correlation of observations within a group/cluster. It indicates the dependency of observations on the group/cluster they belong to. Mathematically, it is calculated as the variance between groups/clusters divided by the total variance (which is variance between groups plus variance within groups). Thus, the higher the correlation within the groups (meaning less variability within groups/clusters), the lower the variance within groups leading to a higher ICC. The converse is also true, in that the lower the correlation within groups (meaning less variability within groups/clusters), the higher the variance within groups leading to a lower ICC.

Table 2: Power and sample size (total number of symptomatic contacts of index TB patients) estimation

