If we power for a minimum detectable difference of 0.20, a sample of 12 clinics/clusters in a complete stepped-wedge cluster-randomized design with 7 time periods (including the baseline), 6 steps, 2 clusters switching from pre-intervention (control) to post-intervention (treatment) at each step, two levels of ICC (rho-alpha of 0.172 and rho-beta of 0.647 from our pre-trial data), an average of 11 index TB patients per cluster per 2-months' time period, a minimum of 1 symptomatic contact per index TB patient, a total number of index TB patients needed for the trial is 924 which achieves 99% power for a minimum detectable proportion difference of 0.1 between a pre-intervention proportion of 0.2 and a post-intervention proportion of 0.4.

These and other sample size estimates are indicated under Scenario 1 in Table 2, in the upper panel in bold, black font.

We also are proposing sample size calculations for other contingencies. Specifically, we wish to plan for scenarios in which one or both sites in a paired-site cluster do not achieve the expected number of symptomatic contacts patients due to secular events, the whole pair will be excluded from the final analysis. Given the effect of a small number of clusters on the power of SWTs, we see two plausible scenarios namely:

- i. Scenario 2: One pair of clusters is excluded from the final analysis. In this case, the number of steps reduces to 5, the time periods reduce to 6 and the number of clusters reduces to 10. The power estimates for this scenario are presented in Table 2 above, in the middle panel in blue ink.
- ii. Scenario 3: Two pairs of clusters are excluded from the final analysis. In this case, the number of steps reduces to 4, the time periods reduce to 5 and the number of clusters reduces to 8. The power estimates for this scenario are presented in Table 2 above, in the lower panel in purple ink. This is the worst-case scenario. The estimates indicate that this scenario would have 99.8% for a minimum detectable proportion difference of 0.2 between a pre-intervention proportion of 0.2 and a post-intervention proportion of 0.4.

Blinding

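### SAP Table 2 and the 99% and 99.8% power statements do not follow from the SAP's inputs: between-index-patient variance is dropped and the discarded transition block is ignored

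*SAP*

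**What the plan says.** The SAP's power section assumes g = 11 index patients per clinic per 8-week block, m = 1 symptomatic contact per index patient, a clinic-level ICC (rho) of 0.172 and an index-patient-level ICC (rho2) of 0.647. The quoted Stata command includes "binomial complete(1) vartotal(1) p1(0.4) p2(0.6) m(1) k(2) rho(0.172) rho2(0.647"), and the text concludes "We estimate that the trial will conservatively need 924 total symptomatic contacts of index TB patients to achieve a power of 99"%. Table 2 prints 1.0000 for every 12-clinic row; the SAP explains that 100% is reported as 99%.

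For the loss of two clinic pairs (Scenario 3) the Summary says "In this case, the number of steps reduces to 4, the time periods reduce to 5 and the number of clusters reduces to 8", and then "The estimates indicate that this scenario would have 99.8% for a minimum detectable proportion difference of 0.2".

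The SAP's Trial Design section says "We will use a complete stepped-wedge design, including an 8-week transition period for training and initial adoption", and shortly afterwards "Data collected during the transition periods will not be included in the final analysis". The exclusion is repeated under Statistical Methods, part a.

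The planning effect varies. The text before the command has "a pre-intervention proportion of patients completing treatment (p1) of 0.4", rising to 0.6. Table 2 has no such row; it uses 0.20 or 0.25 rising to 0.40, 0.45 or 0.50. The Summary states a minimum detectable difference of 0.20 and then, in the same sentence, "achieves 99% power for a minimum detectable proportion difference of 0.1 between a pre-intervention proportion of 0.2" and 0.4.

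**The concern.** A worst case that keeps 99.8% power with a third of the clinics removed and 440 contacts, at a clinic ICC of 0.172, is surprising enough to recompute. Two features of the inputs also conflict with the result. First, with one contact per index patient no two contacts share an index patient, so rho2 should not affect power, yet it is an active input. Second, the command specifies a complete design although one block per clinic is thrown away; the protocol's Sample Size section calls the same feature incomplete.

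Two things are at stake. The stated N of 924 may not deliver the stated power at the stated inputs. And Table 2 is the SAP's basis for treating exclusion of whole clinic pairs as nearly free. That contingency is not remote: Version 2.0 of the SAP records an Ebola-related pause with movement restrictions affecting two sites. The SAP also says it prevails over the protocol, so these are the operative figures.

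**Working it through.** **Inputs** (SAP power section and Table 2): g = 11, m = 1, rho = 0.172, rho2 = 0.647, two-sided alpha 0.05, two clinics crossing per step, Wald z-test. N = m·g·T·K = 1 × 11 × 7 × 12 = 924; 660 and 440 follow for 10 and 8 clinics.

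**Model.** Generalised least squares with fixed period effects and a clinic random intercept. The covariance of one clinic's period means is v(rho·J + r·I), where J is the all-ones matrix, I the identity, v the binomial variance and r the cell residual. Power = Φ(|P2 − P1|/SE − 1.96).

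**Reproducing Table 2.** With a complete layout, v = P1(1 − P1) and r = (1 − rho2)/g = 0.353/11, all 12 rows match to four decimals. Four rows are not 1.0000 and so discriminate: 0.9999 (10 clinics, 0.25 to 0.45), 0.9983, 0.9948 and 0.9999 (8 clinics; 0.20 to 0.40, 0.25 to 0.45, 0.25 to 0.50). Other variance choices, residuals and readings of rho2 that were tried did not match.

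**Why that residual is wrong.** Under the SAP's definitions the total variance splits into rho (clinic), rho2 − rho (index patient within clinic) and 1 − rho2 (contact within index patient): 0.172 + 0.475 + 0.353 = 1. The Table 2 formula keeps 0.172 + 0.353 = 0.525 and loses 0.475. The cell residual should be

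r = (rho2 − rho)/g + (1 − rho2)/(m·g),

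which at m = 1 is (1 − rho)/g = 0.828/11, and 0.828/0.353 = 2.35. The symptom is visible in the 8-clinic, 0.2 to 0.4 row. At rho2 = 0.172, 0.5, 0.647 and 0.8 the Table 2 formula gives 0.900, 0.985, 0.998 and 1.000, so more clustering raises power. The correct formula at m = 1 gives 0.900 throughout.

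**Residual corrected only** (complete layout, P1 variance): the four discriminating rows become 0.961, 0.900, 0.849 and 0.963.

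**Both corrections.** The layout is a baseline block, six equally spaced crossovers and one missing transition block per clinic. Twelve clinics then span 8 blocks with 7 analysed, and 12 × 7 × 11 = 924 analysed contacts. For 0.2 to 0.4, v is 0.20 as the mean of the two arms' variances or 0.16 from P1 only; for 0.4 to 0.6 both are 0.24. Example: 12 clinics, 0.2 to 0.4, mean-arm SE 0.0554, 0.2/0.0554 − 1.96 = 1.65, power 0.95.

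| Case, g = 11 | SAP | Mean-arm variance | P1 variance |
|---|---|---|---|
| 12 clinics, 0.2 to 0.4 | 99% | 95.1% | 98.1% |
| 12 clinics, 0.4 to 0.6 | 99% | 90.9% | 90.9% |
| 10 clinics, 0.2 to 0.4, shortened layout | 1.0000 | 82.8% | 90.2% |
| 10 clinics, 0.2 to 0.4, all 8 blocks kept | 1.0000 | 89.2% (86–92%) | 94.6% (92–96%) |
| 8 clinics, 0.2 to 0.4, shortened layout | 99.8% | 58.9% | 68.5% |
| 8 clinics, 0.2 to 0.4, all 8 blocks kept | 99.8% | 77.9% (64–86%) | 85.9% (74–92%) |

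The rows with all blocks kept average over which pairs are lost (6 and 15 possibilities), with the range in brackets.

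**N for 99% with 12 clinics.** The smallest g is 16 (P1: 13) for 0.2 to 0.4 and 19 for 0.4 to 0.6. Analysed contacts are 84g: 1,344 (1,092) and 1,596.

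**Simulation check.** Binary data with a mixed model on cluster-period proportions, transition excluded, 1,500 trials per case: 93.9% and 90.5% (12 clinics), 82.5% (10) and 58.8% (8, shortened).

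**The 0.1 in the Summary.** For 0.2 to 0.3 with 12 clinics, even the Table 2 formula gives only 95.3%, so 0.1 is a slip for 0.2.

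**Protocol, secondary.** With ICC 0.043, 7 or 23 contacts per clinic-block and P1 variance, a complete 7-period design without covariates gives 82.9% and 91.1%, matching the stated 83% and 91%. The text, however, says transition and covariates are accounted for. Removing the transition gives 68% and 79% with no covariate gain, rising to 82.8% and 91.2% if covariates are assumed to cut the variance by 30%. The protocol does not state the gain, so neither reading can be confirmed.

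**The case against.** The strongest reply is that the 12-clinic trial is barely affected. For 0.2 to 0.4, correcting the residual alone leaves 99.0% (P1: 99.8%), removing the transition alone leaves above 99.9%, and both together under the P1 variance that Table 2 used give 98.1%. That stands. The clear 12-clinic shortfall is the 0.4 to 0.6 effect in the quoted command, at 90.9%.

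Second, g = 11 is deliberately low against 22.7 observed. The protocol's symptomatic fraction (588/1,764) times the SAP's 2.86 contacts per index patient gives about 0.95, so one symptomatic contact each is reasonable. At g = 22.7, 12 clinics reach 99.9% and 99.7% for the two effects. For 0.2 to 0.4, 10 clinics give 98.5% shortened, and 8 clinics give 87.3% (P1: 93.4%) shortened or 96.7% on average with all blocks kept (range 91.4–99.0%). This removes most of the practical alarm, but it is not the calculation the SAP presents, and the 8-clinic figure still falls short of 99.8%.

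Third, mean-arm variance is a choice. Agreed: both conventions are shown, and the conclusion holds under each.

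Fourth, m = 1 is an average, and the SAP's Summary calls it a minimum, so rho2 would matter if numbers vary. True, but this lowers power further: with Poisson variation (an assumption) the two mean-arm 12-clinic figures are about 83% and 76%.

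**Conclusion.** The concern holds. Table 2 was computed with 47.5% of the outcome variance missing and without the excluded transition block. At the SAP's own inputs 924 contacts give about 95% (P1: 98%) for 0.2 to 0.4 and 91% for 0.4 to 0.6, not 99%. The 99.8% for 8 clinics fails under every corrected version at g = 11; the most favourable two-pair loss with both corrections reaches 92.3%.

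The trial is not shown to be underpowered: 12-clinic power stays above 90% in this layout, expected volume is higher and enrolment is uncapped. What fails is the stated power and the reassurance about losing clinic pairs.

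The figures assume exactly one symptomatic contact per index patient, equal cell sizes, no decay of within-clinic correlation over time, and the original equally spaced schedule, because the modified schedule's figure cannot be read from the text.

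**What to change.** - Rerun Table 2 with residual (rho2 − rho)/g + (1 − rho2)/(m·g), the transition cell missing (8 blocks, 7 analysed per clinic), and a stated variance convention, preferably showing both.
- Replace the claim that 924 is needed for 99% with the recomputed power at 924, and show the observed volume (g = 22.7) on a separate line.
- For Scenarios 2 and 3, say whether the remaining clinics keep all calendar blocks, give the matching figures from the table above, and withdraw 99.8%.
- Describe the design as incomplete, consistent with the excluded transition data.
- State one planning effect, labelled completion of TB evaluation (the primary outcome), and change 0.1 to 0.2 in the Summary.
- In the protocol, state the covariate assumption behind 83% and 91%, or mark those figures as superseded by the SAP.

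The cost is one rerun and text edits. Recruitment, conduct and analysis do not change, and no extra enrolment is proposed. The stated power becomes less favourable.

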Merged datasets will be extracted from CommCare, transferred to Stata, and re-arranged into working analytic files and checked for completeness. We will generate time-slice and exposure variables including the control-intervention exposure defining variable (var), the cluster-month var, cluster-exposure var, exposure-month var, and the exposure-time-cluster variable. The transition period will be excluded from the analysis as indicated in the trial design section 2.1 above.

There are 12 study sites that were assigned into six groups (2 facilities per group) and one group at a time will be switched from the standard pre-intervention to the user-centered implementation strategy during 8-week training and transition intervals in a randomly assigned order. Within each of the 6 groups, cluster-level covariates (outcomes, predictors, and confounders) will be formed by aggregating individual-level participants' data. For every cluster, each outcome (primary, secondary, and implementation) occurring

during the study period will be assigned to that cluster, the exposure condition (pre-intervention or intervention), and the trial month in which it occurred. A group-specific summary measure of the outcome, Y_{ij} (for i exposure and j period) will be calculated as a mean (SD) for continuous and count variables, and mean proportion for binary variables. From the Y_{ij} s, we will then calculate the cluster-period summaries $\Sigma Y_{ij} / n$, where n =number of months in i exposure, and estimate unadjusted period-specific intervention effect (θ) based on these cluster-period summaries.

b. Baseline assessment and trend analysis

Baseline measures of all outcomes will be calculated using data collected in the pre-intervention period months 1 and 2 (Figure 1).

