Version 2.0 Update: It was noted above that on 15 October 2022, the President of Uganda announced Ebola-related public health restrictions preventing public movement in two districts where two study sites are located: Mubende and Kasambya. As a result, the principal investigators immediately paused all new introductions of the study intervention according to the schedule noted above. The effects and the duration of this public health emergency are currently unknown, but they may adversely affect both the implementation of this trial and its outcomes. The alternate analysis plans below may become especially relevant if this outbreak invalidates previous assumptions about participant and/or outcome accrual and feasible analytical approaches.

We face a high-level of uncertainty about how the Ebola outbreak and/or other secular trends will affect participant and/or outcome accrual or prior assumptions about sample size and feasible analytical approaches. Accordingly, we lay out our proposed approach below, based on currently available information and our desire to pre-specify the analysis, while recognizing that there may be need to alter these plans if we encounter problems with the analysis, with appropriate justification. The flexibility of our analysis options highlights a strength of the trial design: that is, its pragmatism in the face of an extreme event.

Individual level data will be collapsed at health facility and cluster levels by trial month in both control and intervention exposure periods to create panel data. We will estimate the difference in primary outcome by comparing control and intervention periods using aggregated data. Two models will be considered namely 1) **Random effects logit model (xtlogit)** for binary dependent outcome where the probability of the outcome is determined by the cumulative logit distribution function and accommodates various correlation structures; and 2) **Random effects GEE model (xtreg, re)**; this model accommodates fewer correlation structures than

the former. Both models allow cluster-level aggregated data to vary across time by cluster. The multivariable model will include cluster-level covariates. We will test various correlation structures and choose the final model using likelihood ratio tests and information criteria (AIC, BIC and QIC).

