3.1.2 Populations and subgroups to be analyzed

a. Populations

- **Intention-to-treat (ITT):** The primary analysis will consider the intention-to-treat population, including all index patients eligible at all sites and their identified and screened contacts. Pre-intervention patients in the intention-to-treat population will be those who were diagnosed at a site during the pre-intervention period, and subsequently, their contacts will be considered pre-intervention contacts. Intervention period patients in the ITT population will be those who were diagnosed with TB at a site during the intervention period, and subsequently, their contacts will be considered intervention contacts.
- A per-protocol analysis is not relevant in this case since all community health workers at the site during the intervention period will be exposed to the user-centered implementation strategy, and it is not possible to quantitatively measure adherence to the implementation components in the context of the pragmatic features of the trial.

b. **Adjusted analyses:** In the presence of secular trends (and thus analysis at the individual level), the adjusted analyses will consider age (continuous), sex, HIV status, and any other baseline characteristics found to be imbalanced between control and intervention periods. In the absence of secular trends (and thus aggregated analysis by site and by month), the adjusted analyses will consider covariates such as the proportion of male vs. female, mean age, health center level, health center location (peri-urban vs. rural), and GDP of health center district (low vs. high). Data will be collapsed by the sum of total outcomes for binary outcome variables and mean value for any continuous variables (e.g., age). We will adjust for trial period as appropriate for stepped wedge trial data analysis.

c. **Subgroup analyses:** In the case of individual patient data analysis, five subgroups will be analyzed using the ITT population.

- Age
- Sex: All eligible patients at randomized health centers will be divided into two groups by sex and analyzed separately.

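### The SAP's power section says that a whole randomised pair will be excluded after an accrual shortfall, the primary ITT population keeps all sites, and no text says which applies

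*SAP*

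**What the plan says.** The Summary under Power and sample size calculation turns to contingencies with "Specifically, we wish to plan for scenarios in which one or both sites in a paired-site cluster", and the same sentence continues "do not achieve the expected number of symptomatic contacts patients due to secular events, the whole pair will be excluded from the final analysis". Scenarios 2 and 3 then treat one or two pairs as excluded from the final analysis. For Scenario 3, "the number of steps reduces to 4, the time periods reduce to 5 and the number of clusters reduces to 8".

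Section 3.1.2a defines the primary analysis set: "The primary analysis will consider the intention-to-treat population, including all index patients eligible at all sites and their identified and screened contacts". It makes no exception for pairs with low accrual, and it calls a per-protocol analysis not relevant.

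Elsewhere the SAP does state exclusions that apply. Trial Design says "Data collected during the transition periods will not be included in the final analysis", and also excludes patients recruited in the year-end holiday pause. Statistical Methods, part a, repeats the first of these: "The transition period will be excluded from the analysis as indicated in the trial design section 2.1 above". The pair exclusion is not repeated there.

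The Version 2.0 update reports Ebola restrictions "preventing public movement in two districts where two study sites are located: Mubende and Kasambya". Figure 2 puts Mubende in Group 1 with Wakiso, and Kasambya in Group 4 with Mityana. Alternative Statistical analyses says "The alternate analysis plans below may become especially relevant if this outbreak invalidates previous assumptions about participant and/or outcome accrual", and then plans for accrual trouble without dropping any pair.

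**The concern.** An analyst could follow either the power section or section 3.1.2a and say that the choice was pre-specified. The rule that the SAP takes precedence covers conflicts with the protocol, not a conflict inside the SAP.

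If the exclusion were applied, the trigger would be the number of symptomatic contacts. That number is observed after randomisation and is the denominator of the primary outcome. The power section also projects that enrolment may be four-fold higher or more if the strategy is highly effective, so the count is not plainly independent of the strategy. Partner sites with no shortfall would be removed too.

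The paragraph does not say what number is expected, over what period it is counted, or how a secular cause would be established. The figure of 11 index patients per clinic per block, with one symptomatic contact each, is described as a conservative planning value and is not named as a cut-off.

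**Working it through.** **1. The passages side by side**

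| Place in SAP | What leaves the analysis |
|---|---|
| Trial Design | transition periods; holiday-pause recruits |
| Power Summary | whole pairs with an accrual shortfall due to secular events |
| Statistical Methods, part a | transition period |
| Alternative Statistical analyses | no pair |
| 3.1.2a, primary ITT | no site |

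Only the power section drops pairs. It uses the same term, final analysis, that Trial Design uses for an exclusion that does apply.

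**2. The plan's own figures**

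Table 2 uses N = m × g × T × K:
- Scenario 1: 1 × 11 × 7 × 12 = 924
- Scenario 2: 1 × 11 × 6 × 10 = 660
- Scenario 3: 1 × 11 × 5 × 8 = 440

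All three match. The Scenario 3 power of 0.9983 (0.2 to 0.4) is also reproduced, using total variance 0.2 × 0.8 = 0.16 and an index-patient effect held constant across periods. The shared variance per clinic is then 0.16 × [0.172 + (0.647 − 0.172)/11] = 0.0344, and the period-specific variance is 0.16 × (1 − 0.647)/11 = 0.0051.

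These scenarios describe smaller trials with fewer periods. Excluding pairs from this trial would not remove calendar periods, so the contacts left would be 10 × 7 × 11 = 770 or 8 × 7 × 11 = 616.

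**3. What excluding Groups 1 and 4 would remove**

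The trial has 12 × 7 = 84 clinic-blocks. Two pairs hold 4 × 7 = 28, of which 14 belong to Wakiso and Mityana, which are not named as restricted sites.

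**4. Power, as an illustration only**

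Assumptions:
- the SAP's complete seven-period design, with fixed period effects and a clinic random intercept;
- new index patients in each period, with one symptomatic contact each;
- 0.2 to 0.4, two-sided alpha 0.05;
- total variance 0.3 × 0.7 = 0.21;
- the short sites are Mubende and Kasambya, at half accrual throughout.

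With ICC ρ and n contacts per clinic-block, the clinic variance is 0.21ρ and the variance of a clinic-block mean about it is 0.21(1 − ρ)/n. At ρ = 0.172 and n = 11 these are 0.0361 and 0.0158. The SE of the effect comes from generalised least squares, and power = Φ(0.2/SE − 1.96).

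| n per clinic-block | ρ | Clinics analysed | SE | Power |
|---|---|---|---|---|
| 11 | 0.172 | 12, full accrual | 0.0477 | 98.7% |
| 11 | 0.172 | 12, two sites at half accrual | 0.0498 | 98.0% |
| 11 | 0.172 | 8, Groups 1 and 4 excluded | 0.0606 | 91.0% |
| 22.7 | 0.172 | 8, Groups 1 and 4 excluded | 0.0426 | 99.7% |
| 11 | 0.647 | 8, Groups 1 and 4 excluded | 0.0402 | 99.9% |

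For example, 0.2/0.0606 − 1.96 = 1.34, and Φ(1.34) = 0.910. The 22.7 is the SAP's pre-trial mean of index patients per clinic per two-month block; one symptomatic contact for each is an assumption.

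On the original, since revised, schedule with transition blocks removed (eight blocks, n = 11, ρ = 0.172), power is 92% with all clinics kept at half accrual for the two sites, against 79% with both pairs excluded. At n = 22.7 the last figure is about 97.5%.

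**The case against.** The strongest reply is that this is planning text. The lead-in speaks of planning for scenarios. The sentence is ungrammatical, and one missing conjunction would make the exclusion part of the scenario. The section that defines the analysis populations keeps all sites, and the Ebola text drops no pair. Table 2 does not even model exclusion from this trial. All of this stands, and it makes the what-if reading plausible. It does not settle the matter: the clause is declarative, names a trigger, and is echoed in both scenarios.

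Pairing also has a stated rationale. The Randomization section pairs sites partly so that a secular trend affects both alike, which is a reason to treat a pair together. The one documented event, however, named one site in each of two pairs.

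A reader might infer four stronger things that the documents do not support:
- **Groups 1 and 4 are to be dropped.** No shortfall is reported, and no text applies the exclusion to them.
- **The primary result would be biased.** The trigger is limited to secular events, each pair contributes both control and intervention periods, and the four-fold remark concerns exceeding the target. Selection on accrual could still matter, but no bias is shown.
- **The trial would lose adequate power.** The 91% and 79% are low-accrual cases, and the 79% also uses the superseded schedule.
- **No expected count exists anywhere.** Supplement Tables S1-S3 were not available and may hold one, although the power paragraph does not cite them.

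**Conclusion.** The point holds as an unresolved conflict inside the SAP and should be fixed before analysis. One sentence, read as written, removes randomised pairs from the final analysis; the primary population keeps all sites; no text says which governs. If the sentence is a rule, it is not operational as stated in that paragraph, and it would select clinics on the primary-outcome denominator.

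The conflict does not rest on any power figure. Under the assumptions above, keeping two half-accruing sites costs less than one percentage point of power (98.7% to 98.0%), and excluding their pairs costs about eight (98.7% to 91.0%) at the conservative planning volume. At the pre-trial volume, or with 0.647 as the clinic-level correlation, the loss is negligible. Whether any bias would arise, and in which direction, cannot be determined from the documents.

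**What to change.** 1. In the Power Summary, replace the pair-exclusion clause with a statement that Scenarios 2 and 3 are power contingencies only and do not define an analysis set.
2. In 3.1.2a, state that all 12 randomised clinics stay in the primary ITT analysis whatever their accrual. The only exceptions should be calendar-defined and applied without regard to accrual or outcome: the transition periods, the holiday pause, and any Ebola pause.
3. Reconcile Trial Design, which describes a pause of new introductions that extends the study pause, with the Figure 2 caption, which describes pauses in enrolment. The SAP should say whether data from the Ebola pause are excluded, and at which sites.
4. Make any analysis that leaves out Ebola-affected sites or pairs a sensitivity analysis only, defined by site and calendar date.

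The cost is SAP wording plus one optional sensitivity analysis. If the sentence was only ever a what-if, nothing is lost.
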